5.2.6 Post-Treatment Follow-Up (Day 60)

The following procedures will be performed at follow-up visits (Day 60) end of study:

- Blood oxygen saturation
- Assessment of 14 Common COVID-19-related symptoms questionnaire
- Borg Dyspnoea Scale and walk test
- Chest x-ray imaging
- Record Concomitant medications/therapies.
- Quality-of-life assessment SF-36
- PROMIS fatigue and PROMIS sleep disturbance questionnaires
- Record adverse events

5.3 Assessment Methods

Demographic Data

Demographic data will be collected: age, gender, race, height and weight, comorbidities.

Health Check

A health check will be conducted at the clinic at baseline to include the measurement of vital signs (i.e., heart rate, blood pressure, respiratory rate, temperature). A general health check will be conducted Day 1 post-first dose, Day 3, and Day 5 via telephone visit.

Blood Oxygen Saturation (SpO2)

SpO2 will be collected at baseline and Days 7, 28, and 60 using a pulse-oxygen measuring device.

Assessment of 14 Common COVID-19-related symptoms questionnaire

The FDA assessment of 14 Common COVID-19- related symptoms questionnaire will be conducted at baseline, Day 7, Day 28, and Day 60 as follows:

Example items For items 1–10, sample item wording could be: “What was the severity of your [insert symptom] at its worst over the last 24 hours?”	Example response options and scoring*
1. Stuffy or runny nose	
2. Sore throat	
3. Shortness of breath (difficulty breathing)	
4. Cough	None = 0
5. Low energy or tiredness	Mild = 1
6. Muscle or body aches	Moderate = 2
7. Headache	Severe = 3
8. Chills or shivering	
9. Feeling hot or feverish	
10. Nausea (feeling like you wanted to throw up)	
11. How many times did you vomit (throw up) in the last 24 hours **	I did not vomit at all = 0 1–2 times = 1 3–4 times = 2 5 or more times = 3

continued

Table 1, continued

12. How many times did you have diarrhea (loose or watery stools) in the last 24 hours ??	I did not have diarrhea at all = 0 1–2 times = 1 3–4 times = 2 5 or more times = 3
13. Rate your sense of smell in the last 24 hours	My sense of smell is THE SAME AS usual = 0 My sense of smell is LESS THAN usual = 1 I have NO sense of smell = 2
14. Rate your sense of taste in the last 24 hours	My sense of taste is THE SAME AS usual = 0 My sense of taste is LESS THAN usual = 1 I have NO sense of taste = 2

* Note: Score values are included in the table for ease of reference. FDA cautions against including the score values within the response options presented to trial subjects to avoid confusing subjects.

** The response options shown for items 11 and 12 are intended only for use with a 24-hour recall period.

Time to Sustained Recovery

The time to sustained recovery will be evaluated using the FDA Assessment of 14 Common COVID-19-Related Symptoms questionnaire. Time to sustained recovery is defined as the first day on which the patient achieves a state of ‘none’ or ‘0’ using the FDA assessment.

Borg Dyspnoea Scale

Borg Dyspnoea Scale will be conducted at baseline, Day 7, Day 28, and Day 60. This scale asks you to rate the difficulty of your breathing it starts at number 0 where you are breathing is causing you no difficulty at all and progresses through to number 10 where your breathing difficulty is maximal.

Walk Test

A six-minute walk test will be conducted at baseline, Day 7, Day 28, and Day 60. The walk test is conducted as follows:

- Flat, straight corridor 30 m (100 feet) in length
- Turnaround points marked with a cone
- Patient should wear comfortable clothes and shoes
- Patient rests in chair for at least 10 minutes prior to test (ie, no warm-up period)

- Heart rate and pulse oxygen saturation (SpO₂) should be monitored throughout the test
- If the patient is using supplemental oxygen, record the flow rate and type of device
- Have patient stand and rate baseline dyspnea and overall fatigue using Borg scale*^[1]
- Set lap counter to zero and timer to six minutes
- Instruct the patient: Remember that the object is to walk AS FAR AS POSSIBLE for 6 minutes, but don't run or jog. Pivot briskly around the cone.
- Standardized encouragement statements should be provided at one-minute intervals, such as "You are doing well. You have _ minutes to go" and "Keep up the good work. You have _ minutes to go."
- At the end of the test, mark the spot where the patient stopped on the floor
- If using a pulse oximeter, measure the pulse rate and SpO₂ and record
- After the test record the Borg*^[1] dyspnea and fatigue levels
- Ask, "What, if anything, kept you from walking farther?"
- Calculate the distance walked and record

1. *Borg GA. Psychophysical bases of perceived exertion. Med Sci Sports Exerc 1982; 14:377.*
2. *American Thoracic Society. ATS statement: Guidelines for the six-minute walk test. Am J Respir Crit Care Med 2002; 166:111.*

Chest X-Ray Imaging

Chest x-ray images will be taken at baseline and Day 60. The standard chest examination consists of a PA (posterior anterior) and lateral chest x-ray.

Concomitant Medications

Concomitant medications will be collected: prior concomitant medications, concomitant medications through study exit.

Adverse Events

Any documented adverse event. These include but are not limited to the following: cardiac injury, arrhythmia, septic shock, liver dysfunction, acute kidney injury, and multi-organ failure.

Quality-of-Life Assessment SF-36

Quality of life assessment SF-36 questionnaire with 36 questions health survey for subject's general health will be conducted at baseline, Day 7, Day 28, and Day 60.

PROMIS Fatigue and Sleep Questionnaires

PROMIS fatigue and PROMIS sleep questionnaires will be conducted at baseline, Day 7, Day 28, and Day 60.

6 DISCONTINUATION CRITERIA

6.1 Early Discontinuation of the Study

Discontinuation or temporary suspension is allowed for any reason. The Sponsor may suspend or terminate the study due to the development of any new or unexpected life threatening or adverse events, prolonged hospitalization, or other potential grounds for stopping the study. The number of subjects, as well as the types and the grade severity of the adverse events (according to Common Terminology Criteria for Adverse Events (CTCAE)) may trigger the temporary suspension of study product administration pending a safety investigation as follows:

If any nebulization reactions of grade 3 and above (as defined using the CTCAE grading scale version 5.0 or newer) are observed in any patient within 24 hours of product administration, a safety investigation will occur, which may trigger the temporary suspension of study product administration.

It is agreed that for reasonable cause, either the investigator or the Sponsor may terminate this study, provided written notice is submitted at a reasonable time in advance of intended termination; if by the investigator notice is to be submitted to Ampio Pharmaceuticals, Inc., and if by the Sponsor, notice will be provided to each investigator.

If a severe local reaction or drug-related SAE occurs at any time during the study, the DSMB will review the case immediately.

The study will be immediately suspended and no additional Ampion treatments administered pending review and discussion of all appropriate study data by the DSMB if one or more participants develop any of the following adverse events deemed to be possibly, probably, or definitely related to Ampion by the Investigator and/or Medical Monitor, based upon close temporal relationship or other factors:

- Death
- Respiratory deterioration requiring extracorporeal membrane oxygenation (ECMO)
- Anaphylaxis
- Acute adverse reaction at administration of treatment (i.e., sudden change in vital signs)

The study will not be restarted until all parties have agreed to the course of action to be taken and the IRB/EC has been notified.

6.2 Early Discontinuation of Individual Participants

Discontinuation of individual participants is allowed for any reason. Evaluations of participants who discontinue the study early are described in the Schedule of Assessments in [Section 1.2](#).

7 TREATMENT

Participants randomized to the active arm will receive inhaled Ampion through nebulization daily for 5 days. Participants randomized to the control arm will receive placebo through nebulized inhalation daily for 5 days.

Patients will be allocated to a sequentially numbered treatment in accordance with the randomization schedule following confirmation of eligibility and before treatment.

7.1 Dosing and Administration of Study Medication

Study treatment (Ampion or placebo) will be provided as a solution in vials ready for human use and treatment administration. The participant will be trained to self-administer the study treatment. Treatment should start within 24 hours of randomization and should terminate on last treatment day (Day 5).

Study treatment (Ampion or placebo) will be delivered by inhalation using a nebulizer as a 32mL daily dose administered four times daily (8mL per treatment) every four to six hours for five days.

Study treatment (Ampion or placebo) is presented as a sterile liquid in a glass vial. For each use, the contents of are transferred to the drug reservoir in the nebulizer and nebulized continuously until the drug is fully administered.

Study treatment (Ampion or placebo) is aerosolized for inhalation using the Aerogen Ultra handheld nebulizer (Aerogen Limited, Galway, Ireland, FDA 510K K133360), which consists of the Aerogen Pro-X Controller and the Aerogen Ultra handheld unit. The system is a portable medical device for single patient use indicated for aerosolization of physician-prescribed solutions for inhalation. Ampion is nebulized using the continuous setting on the Aerogen controller, and the study drug is nebulized until it is fully aerosolized.

Product administration may be temporarily suspended until resolution if a serious, or sudden side effects are observed. The nature of the event will be evaluated (i.e., allergic; localized; systemic or otherwise) and appropriate measures applied, which may include symptomatic treatment with antihistamines and antiallergic measures, paracetamol (acetaminophen) and/or corticosteroids.

As described in [Section 6.1](#), if any reactions of grade 3 and above (as defined using the CTCAE grading scale version 5.0 or newer) are observed in any patient within 24 hours of product administration, a safety investigation will occur, which may trigger the temporary suspension of study product administration.

7.2 Study Medication Storage and Accountability

Study treatment (Ampion or placebo) should be stored at room temperature (59° – 77°F or 15° – 25°C) in a secure area with restricted access while at the clinic. The Investigator, the clinical site pharmacist, or other personnel authorized to store and dispense investigational product is responsible for ensuring that the investigational product used in the clinical study is securely

maintained as specified by the Sponsor and in accordance with the applicable regulatory requirements.

All investigational product is to be dispensed in accordance with the Investigator's prescription. Study drug stored at home should be stored at room temperature.

It is the Investigator's responsibility to ensure that an accurate record is maintained of investigational product issued. All investigational product not used during the study must be returned to Ampio Pharmaceuticals Inc., or designated representative after study completion.

If any quality issue is noticed upon the receipt or use of an investigational product (i.e., deficiencies in condition, packaging, appearance, associated documentation, labeling, expiry date, etc.), Ampio Pharmaceuticals, Inc. must be promptly notified.

Under no circumstances may the Investigator supply investigational product to a third party, allow the investigational product to be used other than as directed by this clinical study protocol, or dispose of investigational product in any other manner.

7.3 Concomitant Treatments

Any medication used during the study should be recorded. The start and stop dates, total daily dose, route of administration, and indication for all concomitant medications should be recorded.

7.4 Treatment Compliance

Compliance with the investigational product use will be documented.

8 ADVERSE EVENTS

8.1 Definition of an Adverse Event

An adverse event (AE) is defined as any undesired medical occurrence in a patient or clinical investigation patient receiving a pharmaceutical product which does not necessarily have a causal relationship with this treatment. An AE can therefore be any unfavorable sign and unintended sign (including an abnormal laboratory finding), symptom, or disease temporarily associated with the use of a study drug, whether or not related to the study drug.

Assessment of severity of an AE will be rated according to the following categories:

Grade 1 (MILD): The symptom is barely noticeable to the study patient and does not influence performance or functioning. Concomitant medication is not ordinarily indicated for relief of mild AEs.
Grade 2 (MODERATE): The symptom is of sufficient severity to make the study patient uncomfortable and to influence performance of daily activities. Concomitant medication may be indicated for relief of moderate AEs.
Grade 3 (SEVERE): The symptom causes severe discomfort, sometimes of such severity that the study patient cannot continue in the study. Daily activities are significantly impaired or prevented by the symptom. Concomitant medication may be indicated for relief of severe AEs.

Determination of the relationship between the AE and the study drug will be made using the following guidelines:

Unrelated	The adverse event is unlikely to have been caused by study drug.
Possibly related	It is unclear whether the adverse event may have been caused by the study drug.
Related	The adverse event is likely to have been caused by study drug.

8.2 Definition of a Serious Adverse Event

A Serious Adverse Event (SAE) is any untoward medical occurrence that occurs at any dose that:

- Results in death
- Is life-threatening (patient is at immediate risk of death from the event as it occurred)
- Requires hospitalization or prolongation of existing hospitalization
- Results in persistent or significant disability/incapacity
- Results in any congenital anomaly/birth defect

Important medical events that may not result in death, are not life-threatening, or do not require hospitalization may be considered SAEs when, based on appropriate medical judgment, they may jeopardize the patient and may require medical or surgical intervention to prevent one of the outcomes listed in this definition. Examples of such events include allergic bronchospasm requiring intensive treatment or blood dyscrasias or convulsions that do not result in in-patient hospitalization.

Hospitalizations for elective surgery or other medical procedures that are not related to a treatment-emergent AE are not considered SAEs.

8.3 Recording of Adverse Events and Serious Adverse Events

Recording and reporting of adverse events should be in accordance with the FDA's final "Guidance for Industry and Investigators Safety Reporting Requirements for INDs and BA/BE Studies" of December 2012.

Any AE is to be recorded in the eCRF. In order to avoid vague, ambiguous, or colloquial expressions, the AE should be recorded in standard medical terminology rather than the patient's own words. Whenever possible, the investigator should combine signs and symptoms that constitute a single diagnosis.

The existence of an AE may be concluded from a spontaneous report of the patient; from the physical examination; or from special tests e.g., laboratory assessments, where applicable, or other study-specified tests (source of AE).

The reporting period begins from the time that the patient is randomized until study exit or death, whichever should occur first. Any events continuing at study exit will be followed for 30 days or to resolution, or until no improvement is expected, whichever comes first. Any SAE occurring after the reporting period must be promptly reported if a causal relationship to the investigational drug is suspected. If the patient begins a new therapy, the safety reporting period ends at the time the new treatment is started, however, death must always be reported when it occurs during the study period irrespective of intervening treatment.

Each AE is to be evaluated for duration, severity, seriousness, and causal relationship to the investigational drug. The action taken and the outcome must also be recorded.

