3.3 Study Endpoints

3.3.1 Primary Endpoint

Adverse events (AEs) will be evaluated from baseline through Day 60. The primary endpoint is incidence and severity of adverse events (AEs) and serious adverse events (SAEs) from baseline to Day 28 and Day 60.

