5 STUDY PLAN, PROCEDURES, AND ASSESSMENTS

5.1 Study Plan

Patients with confirmed COVID-19 infection will be screened for up to 72 hours from referral to an outpatient clinic. Patients meeting the selection criteria will be approached for consent in the study. If consented, participants will be randomized in one of two groups, active or control. Within each group, participants are randomized 1:1 following an equal allocation to treatment arms to either active or control arms of the study as follows:

Treatment Arm	Investigational Treatment
Active	Ampion Inhalation for 5-days
Control	Placebo Inhalation for 5-days

Participants who have been randomized into the control arm will receive a daily dose (32mL/day) of placebo (saline) inhalation treatment. Participants who have been randomized into the active treatment arm will receive a daily dose (32mL/day) of inhaled Ampion. Inhaled treatment (Ampion or placebo) will be delivered four times daily, every four to six hours using the nebulizer in equally divided doses of 8mL. This treatment regimen is repeated for 5 days.

The health check vital signs and baseline assessments for blood oxygen saturation, assessment of symptoms/questionnaires, mBDS, walk test, and chest x-ray should occur before the first dose of treatment. These tests and the first dose of treatment will occur at the clinic. Treatment for the remainder of Day 1 and Days 2, 3, 4, 5 will occur at home. Health checks, concomitant medications, and adverse events for Day 1 post-first dose and Days 3 and 5 will be collected via telephone visit.

Safety will be assessed by recording adverse events and with a health check during treatment. Safety is assessed by recording adverse events for the length of the study (60 days).

Efficacy will be assessed by recording the effects of inhalation Ampion compared to placebo on the clinical outcomes for participants with prolonged respiratory complications after a COVID-19 infection using the following clinical outcomes: time to symptom improvement, percentage of participants demonstrating improvement, change in Borg Dyspnoea Scale, time to sustained recovery, blood oxygen saturation, a walk test, and chest x-ray. Assessments for clinical outcomes are performed from baseline to Day 7, Day 28, and Day 60.

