8.4 Serious Adverse Event Reporting

8.4.1 Reporting Requirements

Unexpected serious suspected adverse reactions are subject to expedited reporting to FDA. All SAEs must be entered into the eCRF within 24 hours of first knowledge of the event by study personnel. The investigator must provide his/her assessment of the relationship to study drug at the time of the initial report. The entry of an SAE into the eCRF triggers an automatic alert to the clinical research organization (CRO) safety team. The following information must be reported:

- Protocol number
- Site and/or Investigator number
- Patient number
- Demographic data
- Brief description of the event
- Onset date and time
- Resolution date and time, if the event resolved
- Current status, if event not yet resolved
- Any concomitant treatment and medication
- Investigator's assessment of whether the SAE was related to Investigative product or not.

The CRO Safety Associate will contact the site for clarification of data entered onto the eCRF, or to obtain missing information. In the event of questions regarding SAE reporting, the site may contact the appropriate individual as in [Section 8.4.2](#).

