9.3 Data presentation

9.3.1.1 Demographic and Baseline Characteristics:

Demographic (e.g., age, sex, race, ethnicity) and baseline characteristics (e.g., weight, height, comorbidities) summarized using descriptive statistics, overall and by treatment group for the ITT analysis population.

9.3.1.2 Medical History and Physical Examination:

The number and percent of participants with past and current medical disorders at the time of randomization will be presented overall and by treatment group for the ITT analysis population.

9.3.1.3 Concomitant Medications or Treatments:

The number and percent of subjects receiving concomitant medications or therapies prior to and during the study and at the final visit will be tabulated and presented overall and by treatment group for the ITT analysis population.

Concomitant medications/treatments will be summarized using descriptive statistics and will be presented by type of drug (WHO DRUG classification) overall and by treatment group for the

safety and ITT analysis populations. There should be no significant differences in the use of concomitant treatments between groups. All concomitant therapies will be recorded to be able to compare any inadvertent imbalances between the groups.

9.3.1.4 Safety Data:

Safety data will be presented by treatment arm. Safety data will be evaluated by changes in the frequency and severity of AEs. Concomitant medication will be recorded for safety. AEs will be collected from baseline to Day 60. The severity of AEs (mild, moderate, severe), relatedness (related, possibly related, unrelated) along with the duration, action taken, and outcome (e.g., study withdrawal) will also be recorded.

All data collected under this study protocol will be included in the assessment of patient safety. Missing or incomplete AE data will assume greatest relationship to study drug and/or severity.

Remaining safety data will be collected from enrollment until study exit (or death). Safety data will be tabulated and presented overall and by treatment group for the safety analysis population.

9.3.1.5 Efficacy Data:

The efficacy of treatment on the clinical course and outcome of COVID-19 will be evaluated by treatment arm. Summaries will be performed by treatment arm (active or control).

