9.4 Study Endpoints

9.4.1 Primary Endpoint

Adverse events (AEs) will be evaluated from baseline through Day 60. The primary endpoint is incidence and severity of adverse events (AEs) and serious adverse events (SAEs) from baseline to Day 28.

There will be no statistical tests for incidence and severity of AEs. AEs will be tabulated using descriptive statistics and shift tables and presented for safety.

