5 STUDY ENDPOINTS AND ANALYSES

5.1 PRIMARY ENDPOINT

The primary endpoint is incidence and severity of adverse events (AEs) and serious adverse events (SAEs) from baseline to Day 28.

The hypotheses to be tested are:

$$H_0: \pi_A = \pi_S \text{ versus } H_A: \pi_A \neq \pi_S$$

Where π_A and π_S represent the adverse event rates for Ampion and placebo during the first 28 days after randomization.

The difference between Ampion and Placebo will be tested using the appropriate chi-square test or Fisher's exact test utilizing PROC FREQ with the EXACT option, if necessary.

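### Protocol 8.3 ends safety reporting when an undefined new therapy starts, which contradicts AE collection to Day 60 and can remove events from the primary safety endpoint

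*Protocol*

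**What the plan says.** Protocol 8.3 starts the reporting period at randomization and runs it to study exit or death. It then adds an early end: "If the patient begins a new therapy, the safety reporting period ends at the time the new treatment is started". Two duties survive that point. One covers later SAEs: "Any SAE occurring after the reporting period must be promptly reported if a causal relationship to the investigational drug is suspected". The other keeps any death in the study period reportable, whatever treatment has intervened.

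The rest of the plan has no early end:

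- Protocol 5.1 records AEs for the full 60 days.
- Protocol 9.3.1.4: "AEs will be collected from baseline to Day 60".
- Protocol 9.4.1, repeated in SAP 2.3.1 and 8.2: "Adverse events (AEs) will be evaluated from baseline through Day 60".
- Protocol 8.4.1: "All SAEs must be entered into the eCRF within 24 hours of first knowledge of the event by study personnel".
- The schedules in Protocol 1.2 and SAP 14 mark AEs on every treatment day and at Days 7, 28 and 60.

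Safety is the only primary endpoint. Its window runs to Day 28 in Protocol 9.4.1 and SAP 5.1. Protocol 3.3.1 and SAP 2.3.1 give a longer one: "The primary endpoint is incidence and severity of adverse events (AEs) and serious adverse events (SAEs) from baseline to Day 28 and Day 60". SAP 5.1 compares plain proportions that "represent the adverse event rates for Ampion and placebo during the first 28 days after randomization".

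**The concern.** A site whose participant starts another treatment on Day 10 has two instructions that cannot both be followed: stop safety reporting, or continue to Day 60. Sites may choose differently, and up to five are planned.

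If the 8.3 clause is followed, two kinds of event may not reach the database: non-serious AEs, and non-fatal SAEs that the investigator does not suspect to be related. The endpoint counts both. Events never collected cannot be recovered at analysis.

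The undefined term widens the problem. All medication is allowed and recorded (Protocol 7.3). Protocol 8.1 foresees medication for moderate and severe AEs, and Protocol 7.1 foresees symptomatic treatment of sudden side effects. The visit lists in Protocol 5.2.2 to 5.2.6 group medications and therapies in one item. On a broad reading, treating an AE would close that participant's safety record. Because starting a treatment can depend on symptoms or tolerability, any loss could differ between arms.

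**Working it through.** **1. Which events stay reportable once a new therapy starts**

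| Event after the start | Under the 8.3 clause | Under the Day 60 statements and 8.4.1 | Counted by the endpoint |
|---|---|---|---|
| Death in the study period | Reported | Reported | Yes |
| SAE suspected as related | Reported | Reported | Yes |
| Non-fatal SAE not suspected as related | Not required | Reported | Yes |
| Non-serious AE | Not required | Reported | Yes |

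The last two rows are the conflict. The clause cannot be confined to treatment after the study, because its provision for deaths refers to the study period and to intervening treatment.

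**2. Whether the SAP can repair the loss**

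SAP 5.1 uses simple 28-day proportions and gives no rule for censoring or exposure. SAP 6.3 assigns the greatest relationship or severity to AE data that are missing or incomplete; it does not cover follow-up that was never collected. The SAP table of medications started on study (10.3.11.3) is not linked to AE follow-up.

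**3. Follow-up lost per affected participant**

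A start on Day 7 removes 28 − 7 = 21 days of the Day 28 window (75%) and 60 − 7 = 53 days of the Day 60 window (88%). With 15 per arm, one participant is 100/15 = 6.7 percentage points.

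**4. Size, for illustration**

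The documents state no figure to reproduce. All AE, uptake and severity rates below are assumptions.

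*Case A: uptake unrelated to AEs.* Let p be the true 28-day AE incidence and u the share starting a new therapy by Day 28, with constant hazards. Put l = −ln(1 − p) and m = −ln(1 − u). Counted incidence = l/(l + m) × [1 − exp(−(l + m))].

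For p = 0.40, l = 0.511:

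| u | m | Counted incidence |
|---|---|---|
| 0 | 0 | 40.0% |
| 0.20 | 0.223 | 0.696 × 0.52 = 36.2% |
| 0.30 | 0.357 | 0.589 × 0.58 = 34.2% |
| 0.50 | 0.693 | 0.424 × 0.70 = 29.7% |

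Equal true incidence in the two arms then gives these false differences:

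- equal uptake: 0
- 20% against 30%: 2.0 points
- 20% against 50%: 6.5 points (5.0 if p = 0.30, 7.9 if p = 0.50)

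The arm with more uptake looks safer. For comparison, the approximate 95% half-width for a difference with 15 per arm, at a rate of 0.36, is 1.96 × √(2 × 0.36 × 0.64/15) = 0.34, or 34 points.

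*Case B: an AE prompts the new therapy (broad reading).* AEs follow a Poisson distribution with mean l = 0.511, which corresponds to 40% with any AE. Each AE starts a new therapy with probability q. The first AE is always recorded, so any-AE incidence stays at 40%. Recorded AEs per participant = [1 − exp(−lq)]/q:

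- q = 0.5: 0.451 (12% lost)
- q = 1: 0.400 (22% lost)

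If a share s = 0.2 of AEs is severe, true severe-AE incidence is 1 − exp(−ls) = 9.7%. Recorded incidence is ls/k × [1 − exp(−k)], with k = ls + lq(1 − s):

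- q = 0.5: k = 0.307, giving 8.8%
- q = 1: k = 0.511, giving 8.0%

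**The case against.** The strongest reply is that the instructions are one-sided. Section 8.3 itself requires every AE in the eCRF, 8.3.1 requires follow-up of all AEs during the study, 8.4.1 covers all SAEs, and the schedules prompt for AEs at every visit to Day 60. A site would stop only by letting one clause override all of these. This stands as a reason to call the loss possible rather than certain. It does not remove the contradiction: the more unqualified duties there are, the more text the clause conflicts with.

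A second reply is that the plan calls ordinary drugs concomitant, including those given to relieve AEs, so new therapy probably means something narrower. That is a fair reading and weakens Case B, but no text states it. Defining the term narrowly would also still drop events that the endpoint counts regardless of cause.

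A third reply is that the numbers are small. In Case B any-AE incidence, the quantity tested in SAP 5.1, does not move. In Case A equal uptake produces no difference, and 6.5 points needs a 20% against 50% split that nothing in the documents suggests. The study is not powered, and Protocol 9.4.1 plans description only. All of this is correct. The case for change rests on completeness: a safety study with 15 per arm is mainly a record of its events.

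**Conclusion.** The concern holds and the text should be corrected. As written, the 8.3 clause contradicts the AE collection rules for the only primary endpoint. If followed, it would leave out non-serious AEs and non-fatal SAEs not suspected as related. Deaths and suspected-related SAEs are protected.

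Confidence is high in the conflict of wording. Whether data would be lost, how much, and whether unequally by arm, cannot be known from the documents. Under the assumed rates the distortion of any-AE incidence ranges from none to about one participant in 15, well inside sampling error. If AEs lead to new therapy, the loss falls on later events and on severity. Case A assumes that uptake is unrelated to AEs, so it does not measure informative loss.

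**What to change.** Delete the early-end clause from Protocol 8.3 and state instead:

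> AEs and SAEs are collected from randomization to Day 60, or to study exit or death if earlier, in every randomized participant, whether or not a new therapy is started. New therapies and their start dates are recorded in the concomitant medication log.

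Keep the sentence on suspected-related SAEs after the reporting period and the duty to report deaths. Align the eCRF instructions.

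Optionally, add to the SAP a supportive table that flags AEs with onset after a new therapy and gives, per arm, the number with complete AE follow-up to Day 28 and to Day 60.

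The cost is a wording change in the protocol and eCRF instructions and slightly more AE recording. Visits, AE collection and the medication log already run to Day 60, so no visit or procedure is added. The change concerns data collection only and alters no dose or clinical rule.
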